## 6.4. Prior and Concomitant Medications

The World Health Organization Drug Dictionary (WHODD) Version (WHO Drug March 1, 2020, or later version) will be used to classify prior and concomitant medications by therapeutic class and generic name based on Anatomical Therapeutic Chemical (ATC) code level 3.

Prior medication is defined as any medication taken and stopped prior to the first infusion of the study medication. Concomitant medication is defined as any medication used concomitantly with the study drug that were not stopped before the first infusion or used concomitantly after the first infusion, ending 60 days after the last treatment. Partially or incomplete missing prior/concomitant medication start or stop date will be imputed ([Appendix 1](#)).

Both prior and concomitant medication usage will be summarized by the number (%) of subjects receiving the drug within each therapeutic class and ATC code level 3 and preferred term for the SAF. Multiple usage of the same drug by a patient will be counted only once.

In addition, a listing of all medications (prior or concomitant) taken during the course of the study (from screening through the end of study) captured in Concomitant Medication CRF, as well as Non-Drug Therapies CRF will be provided.

Data on concomitant DMD medications administered during the study are collected and analyzed accordingly. Summary of concomitant DMD medications such as types of corticosteroids and duration of corticosteroid will be provided.

To evaluate the use of co-administered medications that are narrow therapeutic CYP substrates, the clinical database of concomitant medication will be searched for presence of narrow therapeutic index cytochrome P450 substrates and summarized. The list of related medications will be finalized before database lock.

## 6.5. Study Drug Exposure and Treatment Compliance

### 6.5.1. Study Drug Exposure

The number and percentage of subjects who receive study medication will be summarized by treatment group for the SAF.

Duration of weekly exposure/treatment is calculated as:

$$\text{Weeks in treatment} = (\text{last dose date} - \text{first dose date} + 1)/7 \text{ (keep 1 decimal place).}$$

Duration of weekly exposure will be tabulated by treatment group for the Safety population.

The number of infusions and average infusion dose amount in mg and mg/kg, any interruption during infusion (Y/N), and reason for missed dose or interruption will be summarized for the SAF analysis set.

### 6.5.2. Treatment Compliance

Dosing for pamrevlumab (or placebo) will be based on subject's body weight, which will be measured at Screening and every 12 weeks thereafter to determine dose for the subsequent 12-week interval. The total dose of pamrevlumab (or placebo) is not to exceed 4.1g per infusion or

to align with the protocol. Subjects weighing more than 117 kg will receive the maximum allowable dose of 4.1g.

Compliance will be calculated as the total amount of dosage (mg) the subject received divided by the total amount of dosage (mg) the subject is scheduled to receive during the participation in treatment.

$$Compliance (\%) = \frac{\text{actual total dosage received (mg)}}{\text{total planned dosage (mg) while actively in treatment}} \times 100$$

Descriptive statistics for study medication compliance will be presented by treatment group for the SAF. Treatment compliance will be summarized as a continuous variable and as a categorical variable (<70%, 70% –<80%, 80% –<90%, and 90% - 100%, >100%).

### 6.6. Efficacy Analyses

The primary and secondary endpoints will be tested using a fixed sequence procedure to preserve the study-wide error rate of 5%. Under the sequential analysis, the primary and secondary efficacy endpoints will be tested in a predefined sequence according to the order listed in Table 1 each at the usual alpha= 0.05 level of statistical significance. The testing will cease when a failure occurs in the pre-determined sequential hypothesis testing and all p-values for the subsequent testing will be considered nominal.

All analyses for efficacy endpoints will be performed for the mITT during the On-Study period (Section 5.3.1.1), unless noted otherwise. Sensitivity analysis on ITT will also be performed on primary and secondary endpoints as supportive evidence.

**Table 1: Testing Sequence of Primary and Secondary Endpoints**

Testing Sequence	Endpoint
1 (primary endpoint)	Change in the total score of Performance of Upper Limb [(PUL) version 2.0], from baseline to Week 52.
2	Change in percent predicted Forced Vital Capacity (ppFVC) from baseline to Week 52, assessed by spirometry.
3	Change in the total score of Mid-level of PUL from baseline to Week 52
4	Change in the grip strength of the hands from baseline to Week 52, assessed by Hand-Held Myometry (HHM).
5	Change in Left Ventricular Ejection Fraction percentage (LVEF %) from baseline to Week 52, assessed by MRI.

#### 6.6.1. Primary Endpoint Estimands and Analyses

The primary efficacy endpoint in this study is defined as Change from Baseline in the total score of Performance of Upper Limb [(PUL) version 2.0] at Week 52.

**PUL 2.0 scale:**

- The PUL 2.0 scale, with maximum total score = 42

- High Level: Shoulder Dimension, 6 items: Max score = 12
- Mid-level: Elbow Dimension, 9 items: Max score = 17
- Distal level: Wrist and Hand Dimension, 7 items: Max score = 13

Only 1 item in each domain is allowed missing. The score of the missing item will be imputed by the mean of the non-missing items in the domain. If the total score of any domain is missing (the high-level domain only applies to subjects with Item A score  $\geq 3$ ), then the total score will be missing. The total score of PUL is the sum of the total scores of the three domains (if Item A score  $\geq 3$ ) or two domains (Mid-level and Distal level, if Item A score  $< 3$ ).

The last measurement prior to first dose of study drug from Muscle Function Tests (MFTs) at Day 1 will be used to establish baseline.

The primary efficacy endpoint will be analyzed using mITT as the primary analysis set.

The hypothesis to be tested for the primary efficacy analysis is:

**H0:** Change from Baseline in the total score of PUL at Week 52 for the pamrevlumab arm = Change from Baseline in the total score of PUL at Week 52 for the placebo group

Versus:

**H1:** Change from Baseline in the total score of PUL at Week 52 for the pamrevlumab arm  $\neq$  Change from Baseline in the total score of PUL at Week 52 for the placebo group

H0 will be tested at the two-sided alpha = 0.05 level of significance and will be rejected if the p < 0.05 from the test.

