13	Stack of three cans “Stack these two cans, one at a time on the middle can using one hand”	Unable to stack third can even with compensation	Able to stack third can with compensation	Able to stack third can without compensation
14	Stack of five cans “Stack these two additional cans, one at a time on top of this can using one hand”	Unable to stack fifth can even with compensation	Able to stack fifth can with compensation	Able to stack fifth can without compensation

15	Remove lid from container “Use your hands to open this container”	Unable	Opens completely	
----	--	--------	------------------	--

[figure not shown]
Distal wrist and hand Dimension: Do these tests on all individuals				
Item	Description	0	1	2
16	Tearing paper “Tear the sheet of paper beginning from here”	Unable	Tears the sheet of paper folded in half from the folded edge	Tears the sheet of paper folded in 4, beginning from the folded edge
17	Tracing path “Use your pencil to complete the path in one smooth movement”	Unable	Completes the path with compensation - needs to raise pencil from paper or pivot arm	Able to complete the path without stops or raising hand from paper
18	Push on light “Push on the light with the fingers of one hand”	Unable	Able to turn the light on momentarily with fingers of one hand	Able to turn the light on permanently with fingers of one hand
19	Supination “Pick up the light and turn your hand over”	Unable	Picks up the light but either turns hands over incompletely or uses compensation to turn it over	Picks up the light, and turns the hand over completely with no compensatory movements
20	Picking up coins “Using one hand, Pick up 6 coins, one at a time”	Cannot pick up one coin	Can pick up one coin/ token	Can pick up six coins in one hand
21	Placing finger on number diagram (precision not essential) “Using one finger to touch each number on the diagram”	Cannot raise the finger or slide it on the diagram	Able to place finger (slide or lift) between at least two squares	Able to place finger successively on the numbers of the diagram (with or without compensation)
22	Pick up 10g weight finger pinch “Pick up this small weight like this (by body of weight)”	Unable	Able to grip and lift weight off surface	

Total Score PUL	
-----------------	--

Additional Material  
 Item 17: Tracing a path

Item 21: Placing finger on number diagram  
 Instruction: Starting on the yellow number 1 point to the numbers 1 to 10 in turn following the arrow

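### The rule for a missing PUL item ignores that items 15 and 22 are scored 0 or 1 only, so it can give scores above the scale's own maxima

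*SAP*

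**What the plan says.** SAP section 6.6.1 (PUL 2.0 scale) defines the derivation of the primary score. It sets the scale limits: "The PUL 2.0 scale, with maximum total score = 42", made up of "High Level: Shoulder Dimension, 6 items: Max score = 12", "Mid-level: Elbow Dimension, 9 items: Max score = 17" and "Distal level: Wrist and Hand Dimension, 7 items: Max score = 13".

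It then deals with incomplete assessments: "Only 1 item in each domain is allowed missing", and "The score of the missing item will be imputed by the mean of the non-missing items in the domain". No cap, rounding or adjustment to the range of the missing item is stated.

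SAP Appendix 3 gives the scoring sheet. Items 15 and 22 have no category for a score of 2. Item 15, "Remove lid from container", has as its top category "Opens completely", scored 1; item 22, the pinch lift of a 10 g weight, also stops at 1. All other items run from 0 to 2. On every item the 0 category is inability to do the task.

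The resulting score is the primary endpoint. The mid-level domain score is also a secondary endpoint, third in the testing sequence (SAP Table 1), and PUL enters each of the composite z-scores (SAP section 6.6.2.4).

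**The concern.** A plain mean of the other items treats all items in a domain as if they shared one range. In the mid-level and distal domains they do not. The imputed value for a 0/1 item can therefore be a score that the item cannot take, and the domain and total can pass the limits that the same section states. A value imputed for a 2-point item is in turn pulled down, in a high scorer, by the 1-point item in the mean.

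The rule also takes no account of difficulty. Items 9 to 11, for example, move 100 g, 500 g and 1 kg, so a missing item receives the average of tasks that may be easier or harder than itself.

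At stake is the derivation of the primary endpoint and of a tested secondary endpoint. None of the sensitivity analyses in SAP section 6.6.1.2 changes the item rule. Their imputation analyses concern missing visit scores, so they would not show whether it matters. The SAP plans no count of imputed items.

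**Working it through.** **Inputs.** Item ranges: SAP Appendix 3. Domain maxima, the one-missing-item limit and the mean rule: SAP section 6.6.1. Planned difference 2.0 and SD 2.9: SAP section 3.3.

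**The plan's own figures.**
- High level: 6 × 2 = 12.
- Mid-level: 8 × 2 + 1 = 17.
- Distal: 6 × 2 + 1 = 13.
- Total: 12 + 17 + 13 = 42, as stated. The maxima are 17 and 13, not 18 and 14, because of items 15 and 22.
- The sample size also reproduces: by the exact two-sample t-test, power is 90.5% with 46 per arm and 87.0% with 41 per arm. These figures do not depend on the item rule.

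**When a 0/1 item is imputed above 1.** Let S be the sum of the other items in the domain.
- Item 15: imputed value S/8, above 1 when S ≥ 9 of 16 (9/8 = 1.125).
- Item 22: imputed value S/6, above 1 when S ≥ 7 of 12 (7/6 = 1.167).
- Beyond these thresholds the error is upward whatever the true item score, since that score cannot exceed 1.

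**When the domain passes its maximum.**
- Mid-level, item 15 missing: S + S/8. With S = 16 this is 16 + 2 = 18, above 17. With S = 15 it is 16.875, within range.
- Distal, item 22 missing: S + S/6. With S = 12 this is 12 + 2 = 14, above 13. With S = 11 it is 12.833, within range.
- Total with both missing and full scores elsewhere: 12 + 18 + 14 = 44, above 42.

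An out-of-range item value therefore needs only a moderately high score on the other items, whereas an out-of-range domain score needs full marks on all of them. High-level items all share the range 0 to 2 and cannot exceed it.

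**Full scorers missing a 2-point item.**
- Mid-level: (17 − 2)/8 = 1.875, domain 16.875 instead of 17.
- Distal: (13 − 2)/6 = 1.833, domain 12.833 instead of 13.

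**Direction in general.** With k items, true domain total T and true item score x, the error is (T − x)/(k − 1) − x = (T − kx)/(k − 1). It is positive only if x is below the domain average T/k. Summed over the k items it is (kT − kT)/(k − 1) = 0 for every score pattern. Enumerating all patterns gives a range of −2 to +2 in each domain.

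An assumed mid-level pattern for items 7 to 15 of 1, 2, 2, 1, 0, 0, 1, 0, 1 (T = 8) shows both signs:
- item 11 (1 kg, true 0): 8/8 = 1.0, error +1.0;
- item 9 (100 g, true 2): 6/8 = 0.75, error −1.25.

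**Size in the treatment comparison.** The documents give no rate of missing items. Assume 5% or 10% of subjects affected at Week 52 in one arm only, each by +1 or +2 points:
- smallest: 0.05 × 1 = 0.05 points, 2.5% of 2.0;
- largest: 0.10 × 2 = 0.20 points, 10% of 2.0.

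With equal rates and equal errors in both arms the expected shift is 0.

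**The case against.** The strongest case on the other side is that this is a rare edge case with no demonstrated effect on the result. Several parts of it stand.

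- A patient who cannot do an item scores 0 and is not missing, so the natural route to missing hard items is closed. High-level items withheld from patients with an entry score below 3 are handled separately.
- Evaluators must pass a proficiency test, and video quality control is planned at Screening, Day 0 and Week 52 (Protocol section 6.2.4). Missing items may be few.
- The rule is the same in both arms of a double-blind trial.
- The primary random coefficient model fits a line through all post-baseline assessments, so an error at one visit is not the error in the Week 52 estimate.
- A total of 44 needs a patient with full marks elsewhere who misses exactly items 15 and 22.

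A reader might infer that the rule inflates the primary total and hides loss of function. The documents do not support this. The error takes either sign and cancels over the items of a domain. Net inflation would require hard or 0/1 items to be missed more often, which nothing in the documents indicates. An inflated baseline would exaggerate the decline rather than hide it.

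A reader might also want a missing harder item capped at the score of the easier item in its series. That would lower scores only, with no matching floor for easy items, and would not repair the worst case: if the missing item's true score is 0 and all others are 2, the cap is 2 and the error stays +2.

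What the objection does not answer is that the written rule contradicts the maxima stated in the same section.

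**Conclusion.** The point holds as a specification error in the derivation of the primary and Mid-level PUL scores. The out-of-range results (an imputed item as high as 2 on a 0/1 item, domains of 18 of 17 and 14 of 13, a total of 44 of 42) follow from the SAP alone and need no assumption about missingness to be possible. The under-scoring of full scorers, by 0.125 mid-level or 0.167 distal, follows in the same way.

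No net bias in the treatment difference is shown. The expected effect is small: 0.05–0.20 points under the one-arm assumption above, and zero if rates and errors are equal in both arms. A per-patient error of 1 or 2 points at one visit should not be set directly beside the planned between-arm mean difference of 2.0. The case for acting is that the written rule breaks its own scale and is cheap to correct, not that the trial's conclusion is at risk.

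**What to change.** In SAP section 6.6.1, replace the mean rule by: imputed score = maximum of the missing item × (sum of observed item scores in the domain ÷ sum of the maxima of those items).

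Checks for a full scorer:
- item 15 missing: 1 × 16/16 = 1, domain 17;
- item 22 missing: 1 × 12/12 = 1, domain 13;
- a 2-point mid-level item missing: 2 × 15/15 = 2, domain 17;
- a 2-point distal item missing: 2 × 11/11 = 2, domain 13.

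The ratio cannot exceed 1, so domain scores cannot exceed 12, 17 and 13. High-level imputation is unchanged, because all its items share one maximum.

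Rescaling secures the range but not accuracy, since unequal item difficulty remains. On the assumed pattern above, a missing item 11 would receive 2 × 8/15 = 1.07 (true 0), and a missing item 15 would receive 1 × 7/16 = 0.44 (true 1; the plain mean gives 7/8 = 0.875). For that reason, also add a table of the number of imputed items by arm and visit, which would show whether the rule had any influence.

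The cost is one sentence in the SAP, one line of derivation code and one small table, with no new data. SAP section 1 already provides for documenting major modifications after sign-off, in an SAP amendment or the study report.

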### **6.6.1.1. Primary Analysis with the Random Coefficient Model (RCM)**

#### **6.6.1.1.1. Estimand Strategy**

The primary estimand is intended to provide a population level estimate of the treatment effect of the pamrevlumab on a continuous endpoint, regardless of participant compliance with the IP dosing. Treatment policy strategy will be implemented, which means all observed measurements after randomization will be used in the primary analysis.

#### **6.6.1.1.2. Population of Interest**

The mITT population will be used as defined in [Section 5.2.2](#).

#### **6.6.1.1.3. Intercurrent Event Handling**

Treatment discontinuation (such as due to adverse event, lost to follow-up, withdrawal by subject, physician decision, protocol deviations, etc.): Missing data will be implicitly imputed under missing at random assumption.

Death: The worst postbaseline score of all patients in the mITT population would be used to impute all missing values due to death. Missing study day will be imputed as target day of the corresponding analysis visit.

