### 3.3. Sample Size Determination

This section is updated based on latest publications and the study enrollment.

This study is planned to enroll a total of approximately 92 subjects with a 1:1 randomization ratio of assigning to pamrevlumab or placebo, respectively. With Performance of Upper Limb (PUL) version 2.0, the sample size of 92 subjects is needed to detect a treatment difference of 2.0 between treatment arms in change from baseline in the total score of PUL at Week 52, assuming a standard deviation of 2.9 with a 90% power, based on a two-sided two-sample t-test at the alpha level of 0.05. A sample size of 82 subjects will provide the study with at least 85% power to detect the same assumed treatment difference.

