#### 6.6.1.1.4. Analysis Variable

Change from baseline in the total score of all PUL assessments in the randomization treatment period, including scheduled, unscheduled, and available assessments after treatment discontinuation, up to the targeted week 52 during the On-Study period ([Section 5.3.1.1](#)), will be included in the analysis.

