#### 6.6.1.2.2.2. Population of Interest

ITT population will be used as defined in [Section 5.2.1](#).

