**6.6.2.1.1.3. Intercurrent Event Handling Strategy**

Same as [Section 6.6.1.1.3](#)

**6.6.2.1.2. Analysis Variables****6.6.2.1.2.1. Change in Percent Predicted Forced Vital Capacity (ppFVC) from baseline to Week 52, assessed by spirometry****6.6.2.1.3. Change in the total score of Mid-level of PUL from baseline to Week 52 Population Summary for Treatment Comparison**

Same as [Section 6.6.1.1.5](#).

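### The death rule imputes a worst score where the endpoint is a change, so the penalty depends on the dead subject's baseline; the scale is not stated and the ITT analysis borrows the mITT value

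*SAP*

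**What the plan says.** SAP 6.6.1.1.3 leaves data missing after treatment discontinuation to the model under missing at random. For death it sets a value: "The worst postbaseline score of all patients in the mITT population would be used to impute all missing values due to death". The missing study day becomes the target day of the visit, so every planned PUL visit after the death (from Weeks 16, 28, 40 and 52) receives that value.

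SAP 6.6.1.1.4 defines the analysed variable as "Change from baseline in the total score of all PUL assessments in the randomization treatment period". SAP 5.3.2 computes change by subtracting the subject's own baseline, and the MI ANCOVA text in 6.6.1.2.3.5 says the same for imputed values. The primary model (6.6.1.1.5) adjusts for the PUL entry item, not for baseline PUL total, and its sample code estimates covariance separately by arm.

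For the ITT analysis, 6.6.1.2.2.2 says "ITT population will be used as defined in" 5.2.1, while 6.6.1.2.2.3 takes over the death rule unchanged, with the mITT as its reference set. The rule also passes by cross-reference to:

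- the MMRM, MI ANCOVA, jump-to-control, tipping-point and on-treatment analyses (6.6.1.2.1.3, 6.6.1.2.3.3, 6.6.1.2.4.3, 6.6.1.2.5.3, 6.6.1.2.6.3);
- ppFVC and Mid-level PUL, under "Intercurrent Event Handling Strategy" in 6.6.2.1.1.3, then grip (6.6.2.2.1.3), LVEF (6.6.2.3.1.3) and the composite (6.6.2.4.1.3).

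On power, SAP 3.3 plans for 92 subjects to "detect a treatment difference of 2.0 between treatment arms in change from baseline in the total score of PUL at Week 52". Its remaining inputs are an SD of 2.9, 90% power and a two-sided t-test at 0.05. For the smaller set it states: "A sample size of 82 subjects will provide the study with at least 85% power". Section 7 puts power at 87% for 82 mITT subjects. Neither statement allows for deaths.

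**The concern.** If the imputed value is a raw total, two subjects who die on the same day get different changes only because they started at different levels. The entry item removes little of this, since subjects with the same entry score can have quite different totals. Set against a planning SD of 2.9, a penalty in the tens of points is an extreme outlier that moves its arm's mean and inflates that arm's variance.

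A second problem sits in the ITT analysis. Subjects with entry score 1 are excluded from the mITT and have lower function. If such a subject's baseline lies at or below the worst mITT score, his death is recorded as no loss or as improvement.

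Most analyses meant to test the primary result carry the same rule, so they cannot show whether the result depends on it. For ppFVC, grip and LVEF the SAP does not say what a worst score means.

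**Working it through.** **1. The plan's own figures.** Two-sided two-sample t-test, difference 2.0, SD 2.9, alpha 0.05 (SAP 3.3). Noncentrality is (2.0/2.9) × √(n/2). With n = 46 per arm it is 3.31 and power is 90.5%. With n = 41 it is 3.12 and power is 87.0%. Both stated figures reproduce.

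**2. The penalty.** Imputed change = worst score − own baseline. If the worst score were 0, the penalty would equal the whole baseline: at most 30 points for entry score 2 (Mid-level 17 + Distal 13) and at most 42 for entry scores 3 to 6.

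**3. One pamrevlumab death by hand.** Assume a placebo mean change of −2.5, so an active mean of −0.5, and a penalty of −20.

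- Mean shift: (−20 + 0.5)/41 = −0.48, so the difference falls from 2.0 to 1.52.
- Variance of that arm: (39 × 2.9² + 19.5² × 40/41)/40 = (328 + 371)/40 = 17.5, an SD of 4.2 in place of 2.9.
- Standard error: √((17.5 + 8.4)/41) = 0.79, giving a ratio of 1.52/0.79 = 1.9 against a critical value near 2.0. Power is a little under one half; simulation gives 47%.

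**4. Fixed penalties, simulated.** 41 per arm, 40,000 trials, placebo mean −2.0 to −4.0:

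| Penalty | Pamrevlumab death only | Placebo death only | One in each arm |
|---|---|---|---|
| −6 | 81–84% | about 89% | 85–86% |
| −20 | 45–52% | about 92% | 59–65% |
| −30 | 15–20% | about 90% | 26–33% |

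**5. Penalties drawn from assumed baselines.** Uniform baselines, Welch t-test on Week 52 change, and the worst score taken from the simulated trial itself. With baselines 12 to 38 the mean is 25 and the average penalty is about −18, so the worst score is near 25 − 18 = 7; the 5th to 95th percentiles of the penalty are about −30 to −6. The average worst change is about −9.

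| Deaths | Score rule, 12–38 | Score rule, 15–30 | Worst-change rule |
|---|---|---|---|
| None | 87% | 87% | 87% |
| One, pamrevlumab | 51% | 66% | about 77% |
| One per arm | 60–62% | 74–75% | about 82% |
| One, placebo | about 91% | about 91% | about 90% |

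For a placebo death at −18 the estimate moves by (18 − 2.5)/41 = 0.38, from 2.0 to about 2.4 in the drug's favour.

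**6. Timing, under a random coefficient model** (random intercept and slope, assumed residual SD 1.5, placebo mean −2.5, 89% with no death). A pamrevlumab death before Week 16 gives 85% at −6, 49% at −20 and 17% at −30. A death after Week 40, with only Week 52 imputed, gives 87%, 69% and 45%. A slope-only random effect, as in the sample code, shows the same broad pattern in a small run of 250 trials.

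**The case against.** The SAP never writes raw. The word score could be taken to mean change score, and the first defect is then an ambiguity. That stands, although 5.3.2 and 6.6.1.2.3.5 make the raw reading the natural one.

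Giving every death the same worst state is a coherent policy, and dependence on baseline then follows from analysing change. This also has force: with a worst-change penalty near −9, a subject who starts at 38 and dies is scored at about 29, possibly above some survivors.

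No death rate is given, and if nobody dies the rule does nothing. Entry criteria (ppFVC 45 to 85, LVEF at least 50%, no NYHA III–IV heart failure, less than 16 hours of ventilation) select fitter subjects without ruling deaths out.

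Two planned analyses are in practice free of the rule. The per-protocol set (SAP 5.2.3) excludes early terminators, and the cumulative loss of function analysis (6.6.1.2.8.3) censors at discontinuation. They give partial protection.

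A reader might also infer that the step created by a death would produce the residual pattern that switches the primary model to MMRM under 6.6.1.1.5. That is untested, and one outlier among about 82 subjects is not clearly a systematic pattern.

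**Conclusion.** The point holds, as something that should be fixed. On the natural reading the death penalty in the primary analysis is set by the dead subject's baseline, the scale is not stated, and the ITT analysis takes its worst value from a set that leaves out the lower-functioning subjects.

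The size is conditional. Under the assumed baselines, one pamrevlumab death takes power from 87% to about 51% or 66%, where a worst-change rule would leave about 77%. One death per arm gives about 60–62% or 74–75%, against about 82%.

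A reader might infer that any single death undoes the stated power. It does not: a placebo-only death leaves power at about 91% (while favouring the drug), a −6 penalty on pamrevlumab leaves 81–84%, and late deaths cost less than early ones. Nor is a penalty range of −6 to −30 a figure from the documents; it follows from baselines assumed to run from 12 to 38. The chance that any of this occurs cannot be computed from the plan.

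The ITT flaw follows from the text, but it concerns a sensitivity analysis and about 15 excluded subjects (SAP Section 7), and nothing shows how often a death would count as a gain.

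**What to change.** Before database lock and unblinding, amend SAP 6.6.1.1.3 to:

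- state the scale, and impute after death the worst observed change from baseline at any post-baseline visit, both arms pooled, among subjects in the set being analysed (mITT worst for mITT, ITT worst for ITT), limited so that the implied score is not below 0;
- apply the same change-scale rule separately to ppFVC, Mid-level PUL, grip and LVEF, and through them to the composite;
- add one rank-based sensitivity analysis with deaths ranked worst, so that the conclusion does not turn on one extreme value.

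The cost is a few sentences, one derivation and one extra analysis. The drawbacks are that a death in a subject with a high baseline is penalised less than under the raw-score rule, and that the limit at 0 brings back some baseline dependence for very weak subjects. One pamrevlumab death still leaves power near 77%, below the stated 85–87%, so the power text should say that it assumes no deaths.
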